7.2.3.2 Events of Clinical Interest

Selected non-serious and serious adverse events are also known as Events of Clinical Interest (ECI) and must be reported within 24 hours to the Sponsor and within 2 working days to Merck Global Safety. (Attn: Worldwide Product Safety; [contact]).

For the time period beginning when the consent form is signed until treatment allocation/randomization, any ECI, or follow up to an ECI, that occurs to any subject must be reported within 24 hours to the Sponsor and within 2 working days to Merck Global Safety if it causes the subject to be excluded from the trial, or is the result of a protocol-specified intervention, including but not limited to washout or discontinuation of usual therapy, diet, placebo treatment or a procedure.

For the time period beginning at treatment allocation/randomization through 90 days following cessation of treatment, or 30 days following cessation of treatment if the subject initiates new anticancer therapy, whichever is earlier, any ECI, or follow up to an ECI, whether or not related to Merck product, must be reported within 24 hours to the Sponsor and within 24 hours to Merck Global Safety.

Events of clinical interest for this trial include:

1. an overdose of Merck product, as defined in Section 7.2.1 - Definition of an Overdose for This Protocol and Reporting of Overdose to the Sponsor, that is not associated with clinical symptoms or abnormal laboratory results.
2. an elevated AST or ALT lab value that is greater than or equal to 3X the upper limit of normal and an elevated total bilirubin lab value that is greater than or equal to 2X the upper limit of normal and, at the same time, an alkaline phosphatase lab value that is less than 2X the upper limit of normal, as determined by way of protocol-specified laboratory testing or unscheduled laboratory testing.*

*Note: These criteria are based upon available regulatory guidance documents. The purpose of the criteria is to specify a threshold of abnormal hepatic tests that may require an additional evaluation for an underlying etiology.

7.2.3.3 Protocol-Specific Exceptions to Serious Adverse Event Reporting.

Efficacy endpoints as outlined in this section will not be reported to Merck as described in Section 7.2.3.- Immediate Reporting of Adverse Events to the Sponsor and to Merck, unless there is evidence suggesting a causal relationship between the drug and the event. Any such event will be submitted to the Sponsor within 24 hours and to Merck Global Safety within 2 working days either by electronic or paper media.

Specifically, the suspected/actual events covered in this exception include any event that is disease progression of the cancer under study.

The Sponsor will monitor unblinded aggregated efficacy endpoint events and safety data to ensure the safety of the subjects in the trial. Any suspected endpoint which upon review is not progression of the cancer under study will be forwarded to Merck Global Safety as a SAE within 2 working days of determination that the event is not progression of the cancer under study

Hospitalization related to convenience (e.g.transportation issues etc.) will not be considered a SAE.

7.2.4 Evaluating Adverse Events

An investigator who is a qualified physician will evaluate all adverse events according to the NCI Common Terminology for Adverse Events (CTCAE), version 4.0. Any adverse event which changes CTCAE grade over the course of a given episode will have each change of grade recorded on the adverse event case report forms/worksheets.

All adverse events regardless of CTCAE grade must also be evaluated for seriousness.

Table 6 Evaluating Adverse Events

An investigator who is a qualified physician, will evaluate all adverse events as to:

V4.0 CTCAE Grading	Grade 1	Mild; asymptomatic or mild symptoms; clinical or diagnostic observations only; intervention not indicated.
	Grade 2	Moderate; minimal, local or noninvasive intervention indicated; limiting age-appropriate instrumental ADL.
	Grade 3	Severe or medically significant but not immediately life-threatening; hospitalization or prolongation of hospitalization indicated; disabling; limiting self-care ADL.
	Grade 4	Life threatening consequences; urgent intervention indicated.
	Grade 5	Death related to AE
Seriousness	A serious adverse event is any adverse event occurring at any dose or during any use of Merck product that:	
	† Results in death ; or	
	† Is life threatening ; or places the subject, in the view of the investigator, at immediate risk of death from the event as it occurred (Note: This does not include an adverse event that, had it occurred in a more severe form, might have caused death.); or	
	† Results in a persistent or significant disability/incapacity (substantial disruption of one’s ability to conduct normal life functions); or	
	† Results in or prolongs an existing inpatient hospitalization (hospitalization is defined as an inpatient admission, regardless of length of stay, even if the hospitalization is a precautionary measure for continued observation. (Note: Hospitalization for an elective procedure to treat a pre-existing condition that has not worsened is not a serious adverse event. A pre-existing condition is a clinical condition that is diagnosed prior to the use of a Merck product and is documented in the patient’s medical history.); or	
	† Is a congenital anomaly/birth defect (in offspring of subject taking the product regardless of time to diagnosis);or	
	Is a new cancer (that is not a condition of the study) (although not serious per ICH definition, is reportable to the Sponsor within 24 hours and to Merck within 2 working days to meet certain local requirements); or	
Is an overdose (whether accidental or intentional). Any adverse event associated with an overdose is considered a serious adverse event for collection purposes. An overdose that is not associated with an adverse event is considered a non-serious event of clinical interest and must be reported within 24 hours to the Sponsor and to Merck within 2 working days..		

Product: MK-3475
Protocol/Amendment No.:

	
Other important medical events that may not result in death, not be life threatening, or not require hospitalization may be considered a serious adverse event when, based upon appropriate medical judgment, the event may jeopardize the subject and may require medical or surgical intervention to prevent one of the outcomes listed previously (designated above by a †).
		
Duration	Record the start and stop dates of the adverse event. If less than 1 day, indicate the appropriate length of time and units		
Action taken	Did the adverse event cause Merck product to be discontinued?		
Relationship to Merck Product	
Did Merck product cause the adverse event? The determination of the likelihood that Merck product caused the adverse event will be provided by an investigator who is a qualified physician. The investigator's signed/dated initials on the source document or worksheet that supports the causality noted on the AE form, ensures that a medically qualified assessment of causality was done. This initialed document must be retained for the required regulatory time frame. The criteria below are intended as reference guidelines to assist the investigator in assessing the likelihood of a relationship between the test drug and the adverse event based upon the available information.
 
The following components are to be used to assess the relationship between Merck product and the AE; the greater the correlation with the components and their respective elements (in number and/or intensity), the more likely Merck product caused the adverse event (AE):
		
	
 
 Exposure	Is there evidence that the subject was actually exposed to Merck product such as: reliable history, acceptable compliance assessment (pill count, diary, etc.), expected pharmacologic effect, or measurement of drug/metabolite in bodily specimen?	
 
	Exposure	Is there evidence that the subject was actually exposed to Merck product such as: reliable history, acceptable compliance assessment (pill count, diary, etc.), expected pharmacologic effect, or measurement of drug/metabolite in bodily specimen?
	Exposure	Is there evidence that the subject was actually exposed to Merck product such as: reliable history, acceptable compliance assessment (pill count, diary, etc.), expected pharmacologic effect, or measurement of drug/metabolite in bodily specimen?	
	
 
 Time Course	Did the AE follow in a reasonable temporal sequence from administration of Merck product? Is the time of onset of the AE compatible with a drug-induced effect (applies to trials with investigational medicinal product)?	
 
	Time Course	Did the AE follow in a reasonable temporal sequence from administration of Merck product? Is the time of onset of the AE compatible with a drug-induced effect (applies to trials with investigational medicinal product)?
Time Course	Did the AE follow in a reasonable temporal sequence from administration of Merck product? Is the time of onset of the AE compatible with a drug-induced effect (applies to trials with investigational medicinal product)?		

 
 Likely Cause	Is the AE not reasonably explained by another etiology such as underlying disease, other drug(s)/vaccine(s), or other host or environmental factors	
 
	Likely Cause	Is the AE not reasonably explained by another etiology such as underlying disease, other drug(s)/vaccine(s), or other host or environmental factors	
Likely Cause	Is the AE not reasonably explained by another etiology such as underlying disease, other drug(s)/vaccine(s), or other host or environmental factors		

Relationship to Merck Product (continued)
	
The following components are to be used to assess the relationship between the test drug and the AE: (continued)
	
	
Dechallenge
	
Was Merck product discontinued or dose/exposure/frequency reduced?
 
If yes, did the AE resolve or improve?
 
If yes, this is a positive dechallenge. If no, this is a negative dechallenge.
 
(Note: This criterion is not applicable if: (1) the AE resulted in death or permanent disability; (2) the AE resolved/improved despite continuation of the Sponsor's product; or (3) the trial is a single-dose drug trial); or (4) Sponsor's product(s) is/are only used one time.)

	
Rechallenge
	
Was the subject re-exposed to Merck product in this study?
 
If yes, did the AE recur or worsen?
 
If yes, this is a positive rechallenge. If no, this is a negative rechallenge.
 
(Note: This criterion is not applicable if: (1) the initial AE resulted in death or permanent disability, or (2) the trial is a single-dose drug trial); or (3) Sponsor's product(s) is/are used only one time).
 
NOTE: IF A RECHALLENGE IS PLANNED FOR AN ADVERSE EVENT WHICH WAS SERIOUS AND WHICH MAY HAVE BEEN CAUSED BY MERCK PRODUCT, OR IF REEXPOSURE TO MERCK PRODUCT POSES ADDITIONAL POTENTIAL SIGNIFICANT RISK TO THE SUBJECT, THEN THE RECHALLENGE MUST BE APPROVED IN ADVANCE BY THE SPONSOR AS PER DOSE MODIFICATION GUIDELINES IN THE PROTOCOL.

	
Consistency with Trial Treatment Profile
	
Is the clinical/pathological presentation of the AE consistent with previous knowledge regarding Merck product or drug class pharmacology or toxicology?

The assessment of relationship will be reported on the case report forms /worksheets by an investigator who is a qualified physician according to his/her best clinical judgment, including consideration of the above elements.
		

Record one of the following
	
Use the following scale of criteria as guidance (not all criteria must be present to be indicative of Merck product relationship).
	

Yes, there is a reasonable possibility of Merck product relationship.
	
There is evidence of exposure to Merck product. The temporal sequence of the AE onset relative to the administration of Merck product is reasonable. The AE is more likely explained by Merck product than by another cause.
	

No, there is not a reasonable possibility of Merck product relationship
	
Subject did not receive the Merck product OR temporal sequence of the AE onset relative to administration of Merck product is not reasonable OR the AE is more likely explained by another cause than the Merck product. (Also entered for a subject with overdose without an associated AE.)
	

Product: MK-3475
Protocol/Amendment No.:

7.2.5 Sponsor Responsibility for Reporting Adverse Events

All Adverse Events will be reported to regulatory authorities, IRB/IECs and investigators in accordance with all applicable global laws and regulations.

8.0 STATISTICAL ANALYSIS PLAN

8.1 Determination of sample size

Retrospective study (S58910):

Between 2005 and 2010, 285 patients with a ER/PR negative breast cancer larger than 2cm were diagnosed and treated with upfront surgery at the Leuven Multidisciplinary Breast Center (University Hospitals Leuven). Two hundred consecutive patients with available tumor tissue and follow-up data will be included in the proposed retrospective study.

Prospective study (S60100):

The assumptions for the sample size are as follows: More than 600 patients with early breast cancers are diagnosed and treated at the Leuven Multidisciplinary Breast Center (University Hospitals Leuven) on a yearly basis. Twenty percent (120 patients) of these breast cancers are ER/PR negative, half of them Her2 negative and half of them Her2 positive. Of the 120 ER/PR negative patients, 25 percent (30 patients) is expected to receive upfront surgery and 75 percent (90 patients) upfront chemotherapy. After upfront chemotherapy 45 percent of patients is expected to have a residual disease larger than 1cm (40 patients). In total, 70 patients are expected to be eligible for the suggested prospective study. Participation of 50 percent of eligible patients would allow inclusion of 34 patients after 1 year.

Approximately 66 percent (400 patients) of all patients treated at the Leuven Multidisciplinary Breast Center have ER positive breast cancer. 10 percent of these ER+ positive patients is expected to be eligible for this trial taking into account the tumour size after neo-adjuvant therapy and a decent expression of TILs on core biopsy. Participation of 50% of eligible patients would allow inclusion of 20 patients after 1 year. Patients will be included until we have reached the total of 54 patients, independent of the amount of patients in the different cohorts

8.2 Statistical analysis plan

Retrospective study:

Product: MK-3475
Protocol/Amendment No.:

Pearson correlations will be used to analyze the association between expression of PD-L1, CD73, Ki67, the amount of TILs, and other relevant functional immunoparameters. Linear regression analysis will be applied to estimate the predictive value of the core needle biopsy expression measurements of PD-L1, CD73, Ki67 and TIL count for the expression of the same parameters in the whole tumor as measured by the surgical resection specimens.

Prospective study:

Changes in biomarker levels within patients between measurements before and after the administration of pembrolizumab will be analyzed using paired t-test or Wilcoxon signed rank test, as appropriate depending on the distribution of the measurements.

Differences in evolutions of biomarker expression between cohorts will be estimated using linear models and presented as the mean difference of the change with 95% confidence intervals.

Statistical analysis will be performed by an experienced biomedical statistician at the Interuniversity Centre for Biostatistics and Statistical Bioinformatics.

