(4) **Objective:** To evaluate whether one administration of pembrolizumab (Keytruda®) causes a significant shift in T-cell subsets in peripheral blood.

Hypothesis: One administration of pembrolizumab (Keytruda®) causes a significant shift in T-cell subsets in peripheral blood.

(5) **Objective:** To evaluate whether baseline PD-L1 expression and amount of TILs are predictive for the effect of pembrolizumab (Keytruda®) and/or response to neo-adjuvant chemotherapy.

Hypothesis: Tumors with a high baseline PD-L1 expression and a high amount of TILs are more likely to respond to pembrolizumab (Keytruda®) and/or response to neo-adjuvant chemotherapy than tumors with a low baseline PD-L1 expression and/or a low amount of TILs.

RETROSPECTIVE STUDY:

(6) **Objective:** To evaluate whether baseline expression of PD-L1, CD73, Ki67 and the amount of TILs can predict distant metastasis free survival.

Hypothesis: Low expression of PD-L1, CD73 and Ki67 and a high amount of TILs are associated with a better distant metastasis free survival.

(7) **Objective:** To evaluate whether there is an association between expression of PD-L1, CD73, Ki67 and the amount of TILs.

Hypothesis: There is an association between expression of PD-L1, CD73, Ki67 and the amount of TILs.

(8) **Objective:** To evaluate whether the immunohistochemical analysis of PD-L1, CD73, Ki67 and TIL count on core biopsy specimens reflects accurately the expression of these markers on tumor resection specimen.

Hypothesis: The immunohistochemical analysis of PD-L1, CD73, Ki67 and TIL count on core biopsy specimens reflects accurately the expression of these markers on tumor resection specimen.

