This phase 0 study allows short-term evaluation of the effect of anti-PD1 therapy in early breast cancer with biomarker determination by comparing histological markers pre-treatment and at surgery.

Changes in biomarkers related to intratumoral immunity and proliferation may provide evidence for biological activity of pembrolizumab (Keytruda®) and may allow the development of a blood-based biomarker to help predict which patients may benefit from Pembrolizumab (Keytruda®) and to monitor therapy response.

To evaluate whether neo-adjuvant chemotherapy can alter expression of biomarkers related to intratumoral immunity and proliferation, patients will also be enquired to provide a new core biopsy after the last dose of chemotherapy.

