4.2.3 Rationale for Endpoints

4.2.3.1 Biomarker Research

PD-L1: Previous studies have shown a correlation between PD-L1 expression and an objective response in patients treated with anti-PD-1/L1 therapy. However this finding is not consistent among all studies. It also raises the question whether clinical decisions regarding the treatment of patients who have failed conventional therapies and for whom no other treatments are available should be based on PD-L1 expression. On the basis of these controversial results, we will evaluate the potential predictive role of PD-L1 expression in tumor cells.

TILs: TILs might be the primary predictors of response to ICP therapy. Tumors with a large amount of TILs are more likely to respond to anti PD-1/L1 therapy.

Ki67: Immunohistochemical assessment of the proportion of cells staining for the nuclear antigen Ki67 has become the most widely used method for comparing proliferation between tumor samples. In spite of consistent data on Ki67 as a prognostic marker in early breast cancer, its role in breast cancer management remains uncertain. Reductions in Ki67 occur in the tumors of most patients receiving systemic treatment, and there is some evidence that there are greater reductions in patients who respond to treatment.

Except from the above mentioned biomarkers will blood and tissue samples be used to study other possible biomarkers and T-cell subpopulations. These tests will be performed in cooperation with KU Leuven laboratories.

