5.0 METHODOLOGY

5.1 Entry Criteria

5.1.1 Diagnosis/Condition for Entry into the Trial

For the retrospective study (S58910)

All breast cancer patients diagnosed and treated at the Leuven Multidisciplinary Breast Center (University Hospitals Leuven) are documented in a clinical-pathological database, containing extensive general and tumor-related information, as well as clinical follow-up such as relapse and cause of death. This database contains data from over 10000 patients and is linked to a tumor and blood bank. For the proposed study patients will be selected from this database based on the following criteria:

- Diagnosed between 2005 and 2010 with non-metastatic primary invasive breast cancer
- Primary surgery in our institution
- Treated with upfront surgery
- ER/PR negative breast cancer (Allred score)
- Primary tumor >2cm
- Stratification for Her2 status evaluated using IHC followed by FISH

For the prospective Phase 0 study

Patients must meet all of the following criteria to be eligible for study entry:

- Non-metastatic newly diagnosed primary invasive carcinoma of the breast
- Primary tumor > 1 cm
- Negative estrogen (ER) and progesterone (PR) receptor status OR
Positive estrogen receptor (ER) status with TIL expression on core biopsy

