5.1.2 Subject Inclusion Criteria

In order to be eligible for participation in this trial, the subject must:

1. Be willing and able to provide written informed consent/assent for the trial.
2. Be ≥ 18 years of age on day of signing informed consent.
3. Be willing to provide tissue from a newly obtained core or excisional biopsy of a tumor lesion if needed. *Newly obtained is defined as a specimen obtained up to 6 weeks (42 days) prior to initiation of treatment on Day 0. Subjects for whom newly obtained samples cannot be provided (e.g. inaccessible or subject safety concern) may submit an archived specimen only upon agreement from the Sponsor.*
4. Have a performance status of 0 or 1 on the ECOG Performance Scale.
5. Have non-metastatic operable newly diagnosed primary invasive carcinoma of the breast that is:
 - a. Histologically confirmed
 - b. ER/PR negative or ER positive breast cancer with TIL expression on core biopsy. ER/PR status will be evaluated with Allred score (semi-quantitative measurement) following ASCO CAP guidelines 2009. TIL count based on the guidelines of the International TILS Working Group on Breast Cancer
 - c. HER2 negative or positive. HER2 status will be evaluated using IHC followed by FISH with dual probe (ASCO CAP guidelines 2013).

- d. Primary tumor size greater than 1 cm, measured by any of clinical examination, mammography, ultrasound or magnetic resonance imaging
 - e. Any clinical nodal status
6. Have evaluable core biopsy for IHC
 7. Be willing to provide plasma/blood samples
 8. After neo-adjuvant chemotherapy (cohort B1 and B2) patients must have residual tumor >1cm and must be willing to provide evaluable new tumor biopsy for IHC
 9. Demonstrate adequate organ function as defined in Table 1, all screening labs should be performed within 14 days of treatment initiation.

Table 1 Adequate Organ Function Laboratory Values

System	Laboratory Value
Hematological	
Absolute neutrophil count (ANC)	≥1,500 /mcL
Platelets	≥100,000 / mcL
Hemoglobin	≥9 g/dL or ≥5.6 mmol/L without transfusion or EPO dependency (within 7 days of assessment)
Renal	
Serum creatinine OR Measured or calculated ^a creatinine clearance (GFR can also be used in place of creatinine or CrCl)	≤1.5 X upper limit of normal (ULN) OR ≥60 mL/min for subject with creatinine levels > 1.5 X institutional ULN
Hepatic	
Serum total bilirubin	≤ 1.5 X ULN OR Direct bilirubin ≤ ULN for subjects with total bilirubin levels > 1.5 ULN

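### Retrospective objective 8 asks whether core biopsy agrees with the resection specimen, but section 8.2 plans only a regression for predictive value; paired differences and limits of agreement are needed

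*Combined protocol and SAP*

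**What the plan says.** Section 3.2, retrospective objective (8), and its hypothesis concern whether immunohistochemistry and TIL count on the core biopsy "reflects accurately the expression of these markers on tumor resection specimen". The markers are PD-L1, CD73, Ki67 and TILs.

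Section 8.2 gives one method for this pair of specimens: "Linear regression analysis will be applied to estimate the predictive value of the core needle biopsy expression measurements", with the same marker on the surgical specimen as the outcome. The Pearson correlations in the same paragraph relate the markers to one another and so belong to objective (7).

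On numbers, section 8.1 says: "Two hundred consecutive patients with available tumor tissue and follow-up data will be included in the proposed retrospective study". It does not say how many of these patients have both a core and a resection specimen.

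On scale, section 4.2.3.1 describes Ki67 as "Immunohistochemical assessment of the proportion of cells staining for the nuclear antigen Ki67". For phase 0, section 5.1.2 (item 5b) refers TIL counting to the international working-group guideline. No scoring scale is given for PD-L1 or CD73. Nowhere is there a paired difference, limits of agreement, an intraclass or concordance coefficient, a kappa, or a threshold for accuracy.

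**The concern.** Whether one specimen accurately reflects another is a question of agreement: how far apart are two readings of the same tumor, and is one systematically higher? A regression of resection on core answers a different question, namely how well core values predict resection values once a line has been fitted.

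The outputs usually quoted from such a regression can look good when agreement is poor. R-squared is unaffected by a constant offset or a rescaling, and it rises when the tumors are more varied, even if each pair of readings is no closer. The slope hardly reacts to a constant offset, although a proportional bias does move it. Under the present wording, objective (8) could be declared met on R-squared and slope without anyone stating the mean bias or the typical difference in an individual tumor.

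The answer also has some use beyond the retrospective study. Phase 0 relies on "biomarker determination by comparing histological markers pre-treatment and at surgery", and every phase 0 patient must "Have evaluable core biopsy for IHC". The retrospective patients were "Treated with upfront surgery", so their paired differences show the core-to-resection shift with no neoadjuvant treatment in between.

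**Working it through.** **What the plan's figure is.** There is no calculation to reproduce for objective (8). The 200 is a count of available cases out of 285 (200/285 = 70%); no precision target or agreement margin is given.

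**Step 1: algebra.** For any constants a and b > 0, the correlation of core with a + b × resection equals the correlation of core with resection. R-squared is therefore blind to a constant shift or rescaling of one specimen (apart from floor and ceiling effects).

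A worked example with assumed values: true marker mean 30, SD 15, independent error SD 7 in each specimen.
- R-squared = [15²/(15² + 7²)]² = (225/274)² = 0.67
- Slope = 225/274 = 0.82
- SD of paired differences = √(7² + 7²) = 9.9, so limits = mean difference ± 1.96 × 9.9 = ± 19.4

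| Case | R-squared | Slope | Mean difference | Limits of agreement |
|---|---|---|---|---|
| No bias | 0.67 | 0.82 | 0 | -19 to +19 |
| Resection 10 points higher | 0.67 | 0.82 | 10 | -9 to +29 |
| Resection 1.5 times core | 0.67 | 1.23 | 15 | -14 to +44 |

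The slope is 0.82 with no bias because core values carry error. Testing slope 1 and intercept 0 would therefore reject true agreement and does not repair the plan.

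**Step 2: simulation on a skewed percentage.** All marker inputs are assumptions. True TIL percentage is lognormal with median 20 and log-SD 0.5, 0.8 or 1.0; error SD is 3, 6 or 10 points per specimen; resection offset is 0, 5 or 10 points. There are 400,000 tumors per cell, with and without clipping to 0-100.

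Main case (log-SD 0.8, error SD 6, clipped):

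| Offset | R-squared | Slope | Intercept | Mean paired difference |
|---|---|---|---|---|
| 0 | 0.87 | 0.93 | 1.8 | 0.0 |
| 5 | 0.86 | 0.92 | 6.9 | 4.8 |
| 10 | 0.86 | 0.90 | 12.3 | 9.7 |

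Over the whole grid, a 10-point offset changes R-squared by at most 0.02 and slope by about 0.05 at most, while the paired difference moves by about 9 to 10 points.

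**Step 3: R-squared does not measure closeness.** At error SD 6 and no offset, the limits stay at ±15.7 to ±16.6 points while R-squared runs from 0.64 to 0.91 with clipped values (0.96 without clipping). In the main case with no offset, about 22% of tumors differ by more than 10 points.

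**Step 4: what the regression does contain.** Mean bias = intercept + (slope − 1) × core mean. In the main case with offset 10: 12.3 + (0.903 − 1) × 26.7 = 9.7. The residual SD is 0.89 to 1.00 times the SD of differences. The plan calls for neither.

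**Step 5: scale.** With multiplicative error (log-SD 0.2 to 0.4 per specimen, no bias), raw-scale limits cover 100% of the third of tumors with the lowest values but only 78% to 83% of the highest third. Log-scale limits cover 94% to 97% in every third. A ratio bias of 1.5 moves the raw slope by 0.13 to 0.35 but R-squared by at most 0.03.

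**Step 6: concordance coefficient.** It runs from 0.59 to 0.995 with no offset and from 0.49 to 0.97 with a 10-point offset (both upper ends come from unclipped runs; clipped, 0.988 and 0.92). It depends on population spread and can hide a bias, so it is not a substitute.

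**Step 7: precision.** The 95% CI half-width is 1.96 × SD/√n for the mean difference and 1.96 × SD × √(1/n + 1.96²/(2(n − 1))) for each limit. With SD of differences 8.2 (main case):

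| Pairs | Mean difference | Each limit |
|---|---|---|
| 200 | ±1.1 points | ±1.9 points |
| 100 | ±1.6 | ±2.8 |
| 50 | ±2.3 | ±3.9 |

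For SD 4.1 to 14.2 at 200 pairs, the half-widths are 0.6 to 2.0 and 1.0 to 3.4 points. Because section 8.1 asks only for available tissue, 200 pairs is the best case.

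**The case against.** The plan never mentions R-squared. It plans a regression, which also yields an intercept and a residual SD; the intercept reacts clearly to an offset (1.8, 6.9, 12.3 in the main case), and bias and spread can largely be recovered. Treating resection as the reference and studying how well a small core predicts it is a legitimate calibration question, so making the regression secondary is partly a matter of preference. The simulation inputs are assumed, and the widest ranges come from unclipped runs in which some percentages exceed 100. A remedy that branches by distribution could itself be loose. The consequence is small.

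Much of this is fair. The defect is missing reporting and a missing criterion, not a model incapable of addressing the question. Regression has a proper place, and the clipped figures are the safer ones to quote. But the information being recoverable does not mean it will be reported, since section 8.2 commits to none of it. The raw intercept is not the bias either: it is 1.8 in the main case when there is none. Nor does calibration say how close is close enough. The insensitivity of R-squared to a shift is algebra and needs no assumed inputs.

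**Conclusion.** The concern holds. Objective (8) is an agreement question and section 8.2 does not plan an agreement analysis or define accuracy. Under the assumed TIL values, a 10-point bias would be nearly invisible in R-squared and slope, and an R-squared near 0.87 is compatible with individual differences of up to about 16 points either way. Those sizes depend on the assumed marker distribution and error; the direction does not.

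The reach is limited to one secondary retrospective objective, and no primary result depends on it. Its help in interpreting phase 0 is mainly for cohorts A1 and A2: by section 8.1, 30 upfront-surgery ER/PR-negative patients a year × 50% participation = 15 of the planned 54, which is a projection because enrolment is not fixed by cohort. The retrospective tumors are also larger ("Primary tumor >2cm", against more than 1 cm in phase 0). The paired analysis would inform the phase 0 comparison but would not correct its test. This should be changed, but it is not critical.

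**What to change.** In section 8.2, for objective (8):

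- Make the main analysis, for each marker, the mean paired difference between core and resection with 95% CI, and the 95% limits of agreement.
- State the scoring scale for each marker, PD-L1 and CD73 in particular, and say whether the TIL guideline cited for phase 0 also applies to the retrospective slides.
- Write down the rule for choosing the scale before the comparison is made. If the spread of differences grows with the level, use a log or similar transformation and say how zeros are handled; if differences are only non-normal, use percentile limits; if the marker is scored in categories, use weighted kappa.
- State in advance, per marker, what difference still counts as accurate.
- Report how many of the 200 patients have both specimens.
- Keep the planned regression as secondary. An intraclass or concordance coefficient is optional and should not stand alone.

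The cost is SAP wording and a little analysis time. The slides and database are the same, and no extra patients are needed.
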